17.4 RSV-related Signs and Symptoms to be Collected

Temperature enter _____

Respiratory Rate enter _____

Coryza None Mild Moderate Severe

Cough None Mild Moderate Severe

Grunting with expiration None Present

Nasal flaring None Present

Retractions None Mild Moderate Severe

Wheezing None Mild Moderate Severe

SpO₂ on room air enter _____

17.5 Dehydration Evaluation – Part of Physical Examination

Dehydration: None Mild 3-5% Moderate 6-10% Severe > 10%

Dehydration%	Mild 3% to 5%	Moderate 6% to 10%	Severe > 10%
Mental status	Normal	Listless, irritable	Lethargy, altered mental status
Heart rate	Normal	Increased	Increased
Quality of Pulses	Normal	Normal to decreased	Decreased to thready
Capillary refill	Normal	Prolonged	Prolonged
Blood pressure	Normal	Normal	Normal to decreased
Respirations	Normal	Tachypnea	Tachypnea, deep
Eyes	Normal	Slightly sunken, decreased tears	Sunken, cries without tears
Fontanelle	Normal	Sunken	Sunken
Urine output	Normal to decreased	Decreased	Oliguric or anuric

Source: [Vega RM, 2019](#)

Note: This is a guide for the investigator. Just enter category, DO NOT enter each factor.

17.6 ReSVinet Scale for Clinicians

Item	0 points	1 points	2 points	3 points
1 Feeding intolerance	No	Mild Decreased appetite and/or isolated vomits with cough.	Partial Frequent vomits with cough, rejected feed but able to tolerate fluids sufficiently to ensure hydration.	Total Oral intolerance or absolute rejection of oral feed, not able to guarantee adequate hydration orally. Required nasogastric and/or intravenous fluids
2 Medical intervention	No	Basic Nasal secretions aspiration, physical examination, trial of nebulized bronchodilators, antipyretics.	Intermediate Oxygen therapy required. Complementary exams were needed (chest X-rays, blood gases, hematimetry...). Maintained nebulized therapy with bronchodilators.	High Required respiratory support with positive pressure (either non-invasive in CPAP, BiPAP or high-flow O ₂ ; or invasive through endotracheal tube).
3 Respiratory difficulty	No	Mild Not in basal situation but does not appear severe. Wheezing only audible with stethoscope, good air entrance. If modified Wood Downes, Wang score or any other respiratory distress score is applied, it indicates mild severity.	Moderate Makes some extra respiratory effort (intercostal and/or tracheosternal retraction). Presented expiratory wheezing audible even without stethoscope, and air entrance may be decreased in localized areas. If modified Wood Downes, Wang score or any other respiratory distress score is applied, it indicates moderate severity.	Severe Respiratory effort is obvious. Inspiratory and expiratory wheezing and/or clearly decreased air entry. If modified Wood Downes, Wang score or any other respiratory distress score is applied, it indicates high severity.
4 Respiratory frequency	Normal < 2 m: 40–50 bpm 2–6 m: 35–45 bpm 6–12m: 30–40 bpm 12–24m:25–35 bpm 24–36m: 20–30 bpm	Mild or occasional tachypnea Presented episodes of tachypnea, well tolerated, limited in time by self-resolution or response to secretion aspiration or nebulization.	Prolonged or recurrent tachypnea Tachypnea persisted or recurred despite secretion aspiration and/or nebulization with bronchodilators.	Severe alteration Severe and sustained tachypnea. Very superficial and quick breath rate. Normal/low breath rate with obvious increased respiratory effort and/or mental status affected. Orientative rates of severe tachypnea: < 2 m: > 70 bpm 2–6 m: > 60 bpm 6–12m: >55 bpm 12–24m: >50 bpm 24–36m: >40 bpm
5 Apnea	No			Yes At least one episode of respiratory pause medically documented or strongly suggested through anamnesis.
6 General Condition	Normal	Mild Not in basal situation, child was mildly uncomfortable but does not appear to be in a severe condition, not impress of severity. Parents are not alarmed. Could wait in the waiting room or even stay at home.	Moderate Patient looks ill, and will need medical exam and eventually further complementary exams and/or therapy. Parents are concerned. Cannot wait in the waiting room.	Severe Agitated, apathetic, lethargic. No need of medical training to realize severity. Parents are very concerned. Immediate medical evaluation and/or intervention were required.
7 Fever	No	Yes, mild Central T < 38.5°C	Yes, moderate Central T > 38.5°C	

(m = months)

## Revision History

Version #	Date (DD-Mmm-YYYY)	Document Owner	Revision Summary
1.0	09-Oct-2020	PPD	Initial Release Version
2.0	14-Jun-2021	PPD	Clarifications and updates prior to Part A analysis

This document is confidential.

This document is confidential.

## 1. Glossary of Abbreviations

Abbreviation	Description
AE	Adverse Event
ALT	Alanine Aminotransferase
ANCOVA	Analysis of Covariance
AST	Aspartate Aminotransferase
AUC	Area Under the Curve
AUC 0-12	Area Under the Plasma Concentration–Time Curve from Zero to 12 Hours
AUC 0-∞	Area Under the Plasma Concentration-Time Curve from Zero to Infinity
AUC 0-t	Area Under the Plasma Concentration-Time Curve from Zero to the Last Measurable Concentration
AUC 0-tau	Area Under the Plasma Concentration-Time Curve from Zero to the End of Last Dosing Interval
BMI	Body Mass index
C 12	Trough Concentration at the End of 1 st Dosing Interval
C ave	Average Plasma Concentration over Dosing Interval
CBIA	Cell-based Infectivity Assay
CL/F	Apparent total body clearance
C max	Maximum Observed Plasma Concentration
C min	Minimum Observed Plasma Concentration
CRF	Case Report Form
CTCAE	Common Terminology Criteria for Adverse Events (AEs)
C trough	Plasma Trough Concentration
CV	Coefficient of Variation
DSMC	Data Safety Monitoring Committee
EC 90	90% of the effective concentration
ECG	Electrocardiogram
ICH	International Conference on Harmonisation
IV	Intravenous
LLoQ	Lower Limit of Quantification
LoD	Limit of Detection

This document is confidential.

**Statistical Analysis Plan for Interventional Studies**

Sponsor: ReViral Ltd; Protocol No.: REVC003

Abbreviation	Description
LRTI	Lower Respiratory Tract Infection
lsmean	Least Square Mean
Max	Maximum
MedDRA	Medical Dictionary for Regulatory Activities
Min	Minimum
mITT	Modified Intent-to-Treat
N/A	Not Applicable
NA	Not Applicable
NCI	National Cancer Institute
PD	Pharmacodynamics
PK	Pharmacokinetics
PT	Preferred Term
Q1	First Quartile
Q3	Third Quartile
RSV	Respiratory Syncytial Virus
RT-qPCR	Reverse Transcriptase Quantitative Polymerase Chain Reaction
SAE	Serious AE
SAP	Statistical Analysis Plan
SD	Standard Deviation
SOC	System Organ Class
SOP	Standard Operating Procedure
$t_{1/2}$	Terminal Half-life
TEAE	Treatment Emergent AE
$t_{max}$	Time to Maximum Plasma Concentration
TFL	Tables, Figures and Listings
V/F	Apparent Volume of Distribution of the Drug after Extravascular Administration
WHO	World Health Organisation

This document is confidential.

## 2. Purpose

The purpose of this statistical analysis plan (SAP) is to ensure that the data listings, summary tables and figures which will be produced, and the statistical methodologies that will be used, are complete and appropriate to allow valid conclusions regarding the study objectives.

### 2.1. Responsibilities

Syneos Health will perform the statistical analyses and are responsible for the production and quality control of all tables, figures and listings (TFLs).

### 2.2. Timings of Analyses

The primary analysis of safety, tolerability, pharmacokinetics (PK) and antiviral effect of RV521 for Parts A, B and C are planned after all subjects from the respective study part complete the final study visit or terminate early from the study. The data will therefore be reported in 3 separate parts.

Interim data summaries will be provided to the independent Data Safety Monitoring Committee (DSMC) according to the DSMC Charter or as requested by the DSMC to allow performance of their duties to monitor the safety of the subjects enrolled in the study.

This document is confidential.

### 3. Study Objectives

#### 3.1. Primary Objectives

To evaluate the safety and tolerability of single (Part A) and multiple (Part B) oral doses of RV521 in infants hospitalised with respiratory syncytial virus (RSV) lower respiratory tract infection (LRTI).

#### 3.2. Secondary Objectives

- To characterise the PK of single (Part A) and multiple (Part B) oral doses of RV521 in infants hospitalised with RSV LRTI. Note that in Spain, this was promoted to a primary objective.
- Part B: To evaluate the antiviral effects of RV521 in infants hospitalised with RSV LRTI.
- Part B: To evaluate the effect of RV521 compared to placebo on the clinical course of RSV infection.

#### 3.3. Exploratory Objectives

- CCI [REDACTED]

[REDACTED]

#### 3.4. Objectives for Part C

- Primary Objective: To evaluate the effect of RV521, compared to placebo, on the clinical course of RSV LRTI.
- Secondary Objectives:
  - Evaluate the safety of RV521 given as a multiple dose regimen.
  - Effect of RV521, compared to placebo, on nasopharyngeal shedding (viral load) of RSV.
  - CCI [REDACTED]
  - CCI [REDACTED]

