7.2 PART C: Objectives and Endpoints

Primary Objectives for Part C	Primary Endpoint

 • Evaluate the antiviral effects of RV521, compared to placebo, on nasopharyngeal shedding of RSV in infants hospitalised with RSV LRTI 	
 • Time-weighted average change from Baseline to Day 7 in RSV viral load measured in nasopharyngeal swabs by RT-qPCR.
Secondary Objectives for Part C	Secondary Endpoints

 • To evaluate virologic parameters derived from the RSV viral load as measured in nasopharyngeal swabs • CCI [REDACTED] 	
 • Virologic parameters derived from the RSV viral load as measured in nasal swabs include but are not limited to: 
 ○ Change from baseline in viral load (RT-qPCR and CBIA) at each time point ○ Time to below viral load quantification limit (RT-qPCR and CBIA) ○ Proportion of subjects with viral load below quantification limit (RT-qPCR and CBIA) at each timepoint throughout the study • CCI [REDACTED]

 To evaluate the clinical efficacy of multiple oral doses of RV521 in infants hospitalised with RSV LRTI Evaluate the safety and tolerability of RV521 given as a multiple dose regimen 	
 Time to resolution in RSV-related symptoms Time to improvement of RSV-related symptoms Reduction in severity of symptoms by RV521, compared to placebo, measured by a composite score over time Use of supplementary oxygen, including, but not limited to, duration and maximum level of O₂ provided Time to normalisation of respiratory rate Safety of RV521 compared to placebo assessed by incidences of AEs, discontinuations due to AEs, SAEs, and clinically significant changes in laboratory tests

Exploratory Endpoints (Part C)
	
 [REDACTED] [REDACTED] [REDACTED]

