8.2 Overall Study Design and Plan: Description

The clinical study consists of 3 parts:

- Part A is an open-label, multicentre, single dose study in infants hospitalised with RSV LRTI
- Part B is a randomised, double-blind, placebo-controlled, multicentre multiple dose study in infants hospitalised with RSV LRTI
- Part C is a randomised 1:1:1, double-blind, placebo-controlled, multicentre, multiple-dose study comparing two dose levels of RV521 to matching placebo in infants ≥ 1 months and ≤ 36 months hospitalised with RSV LRTI

The number of subjects enrolled in Parts A and B of the study will depend on the safety and PK data from the group of subjects enrolled in specified cohorts and the subsequent recommendation of the Data Safety Monitoring Committee (DSMC). The DSMC will review all available safety and PK data collected from the first 3 subjects and subsequent 3 subjects in Cohort 1 and determine the starting dose for subjects in Cohort 2 (either 2 mg/kg or an adjusted dose based on Cohort 1 safety and PK data). The DSMC may recommend a dose adjustment (either a reduction or an escalation) and/or regimen adjustment (Part B only) for subsequent subjects because of the observation of an unexpected safety/tolerability profile and/or differences between the observed and predicted exposure resulting from a specified dose of RV521.

Part A

Part A of the study will be conducted across 2 cohorts and will comprise 2 age groups:

- Cohort 1: subjects ≥ 6 months to ≤ 36 months
- Cohort 2: subjects ≥ 1 month to < 6 months

The proposed starting doses of RV521 of 2.5 mg/kg for subjects ≥ 6 months to ≤ 36 months of age (Cohort 1) and 2 mg/kg for subjects ≥ 1 month to < 6 months of age (Cohort 2) are expected to deliver a specified group mean exposure ($1 \times EC_{90}$ at trough concentration) based on PK modelling and simulation using existing clinical data in healthy adult subjects (CCI [REDACTED] and CCI [REDACTED]) and nonclinical data. Pharmacokinetic data from groups of 3 subjects in Cohort 1 and Cohort 2 will be reviewed to identify any differences between the observed and predicted exposure resulting from a specified dose of RV521. Safety data will be sent to the DSMC for review prior to any dose adjustment.

Enrolment into Part A of the study will commence with the older subjects (Cohort 1).

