11 STATISTICAL METHODS

11.1 Statistical and Analytical Plans

A statistical analysis plan (SAP) will be prepared by Syneos Health as a separate document. The SAP will include a more detailed description of the planned statistical methodologies for each part of the study. The SAP will be finalised before the closure of Part A. Any subsequent SAP amendments applicable to Parts B or C will be signed off prior to database lock and unblinding of the respective parts.

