#### 3.5. Brief Description

The clinical study consists of 3 parts, the third part (Part C) is optional:

- Part A is an open-label, multicentre, single-dose study in infants hospitalised with RSV LRTI.
- Part B is a randomised, double-blind, placebo-controlled, multicentre multiple dose study in infants hospitalised with RSV LRTI.
- Part C is a randomised 1:1, double-blind, placebo-controlled, multicentre, multiple-dose study in infants hospitalised with RSV LRTI.

This document is confidential.

The number of subjects enrolled in Parts A and B of the study will depend on the safety and PK data from the group of subjects enrolled in specified cohorts and the subsequent recommendation of the DSMC.

The DSMC may recommend a dose adjustment (either a reduction or an escalation) and/or regimen adjustment (Part B only) for subsequent subjects because of the observation of an unexpected safety/tolerability profile and/or differences between the observed and predicted exposure resulting from a specified dose of RV521.

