##### Primary Endpoints for Part C

- Time to resolution of symptoms
- Time to improvement of symptoms
- Reduction in severity of symptoms by RV521, compared to placebo, measured by a composite score over time
- Use of supplemental oxygen, including, but not limited to, duration and maximum level of oxygen provided

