##### Secondary Endpoints for Part C

- Safety of RV521 compared to placebo assessed by incidences of AEs, discontinuations due to AEs, SAEs, and clinically significant changes in laboratory tests
- Comparison between RV521 and placebo for changes in viral load over time as for Part B
- CCI [REDACTED]

This document is confidential.

- CCI [REDACTED]

This document is confidential.

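### SAP v2.0 specifies a different Part C from the protocol (one RV521 arm, clinical primary endpoints, RSV-score stratum); an aligned SAP must be signed before Part C database lock and unblinding

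*SAP*

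**What the plan says.** The SAP's revision history dates v2.0 to 14 June 2021 and describes it as "Clarifications and updates prior to Part A analysis". Its Part C primary objective is "Primary Objective: To evaluate the effect of RV521, compared to placebo, on the clinical course of RSV LRTI". Section 3.5 says "Part C is a randomised 1:1, double-blind, placebo-controlled, multicentre, multiple-dose study in infants hospitalised with RSV LRTI". Section 4.4 lists four primary endpoints, all clinical: time to resolution, time to improvement, a composite severity score, and "Use of supplemental oxygen, including, but not limited to, duration and maximum level of oxygen provided". Viral load appears among the secondary endpoints as "Comparison between RV521 and placebo for changes in viral load over time as for Part B".

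The protocol's section 8.2 describes Part C as a 1:1:1 "multiple-dose study comparing two dose levels of RV521 to matching placebo". Its section 7.2 names one primary endpoint: "Time-weighted average change from Baseline to Day 7 in RSV viral load measured in nasopharyngeal swabs by RT-qPCR". Section 8.2 and the synopsis say that this endpoint compares the two dose levels with placebo. Section 11.1.3 asks for analysis of covariance and refers further detail to the SAP.

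On timing, protocol section 11.1 says: "Any subsequent SAP amendments applicable to Parts B or C will be signed off prior to database lock and unblinding of the respective parts".

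**The concern.** The protocol fixes the primary endpoint, the comparison and the type of model, but it names no covariates. The SAP is where the primary model is meant to be fully prespecified, and the SAP supplied does not do that for the current Part C. It places DAVG under secondary pharmacodynamic endpoints. Its adjustment terms follow a randomisation scheme the protocol does not use, and one of them comes from a scale the protocol does not schedule in Part C.

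If this text were still in force at lock, the team would have two choices. It could follow the SAP and contradict the protocol's primary endpoint, or it could choose the primary model without a usable written plan. Either would weaken the main result of the only part of the study with a formal sample size in the current protocol.

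**Working it through.** **Step 1. Reproduce the protocol's sample size (section 11.2).** Inputs: difference 1 log10, SD 1.25, two-sided alpha 0.05, power 90%.

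n per group = 2 × (1.960 + 1.282)² × 1.25² / 1² = 32.8, so 33 by the normal approximation. By the two-sample t-test, 33 per group gives 89.3% and 34 gives 90.2%, which confirms the stated 34. Adding 10%: 34 × 1.10 = 37.4, stated as 37; 3 × 37 = 111.

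**Step 2. Check the totals.** Protocol: 24 + 40 + 111 = 175. SAP: 24 + 40 + 120 = 184. Each agrees with its own document. The two sets of figures belong to two designs; neither is a miscalculated version of the other. (The SAP's 120 rests on time to resolution with no stated distribution and could not be reproduced. Nothing here depends on it.)

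**Step 3. Set the Part C text side by side.**

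| Item | SAP v2.0 | Protocol |
|---|---|---|
| Arms | RV521 v placebo, 1:1 (3.5, 3.9) | two RV521 doses v placebo, 1:1:1 (8.2) |
| Size | about 120, 60 per arm (3.6.1, 3.7) | 111, 37 per arm, 34 evaluable (11.2) |
| Primary | four clinical endpoints (4.4) | RT-qPCR DAVG to Day 7 (7.2) |
| Strata | symptom duration; RSV score (3.8.1) | age group (8.5.4) |
| Clinician scale | RSV Clinical Scoring System (8.1, Table 3) | ReSVinet for clinicians (11.1.5, Table 3a) |
| Wilcoxon | RV521 v placebo (8.3) | each dose v placebo, time to resolution (11.1.5) |
| mITT, fewer than 6 doses | decided at blind review (5.2) | no such step in Part C (11.1.1) |
| Last visit | Day 28 (3.5) | Day 34 (9.4.5, 9.5) |

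**Step 4. Check the models.** The SAP index shows eight unredacted Part C ANCOVA tables: 14.2.1.3.2, 14.2.2.2.2, 14.2.8.3.2.2, 14.2.8.3.2.4 and 14.2.8.3.3.1 to 14.2.8.3.3.4. Their models are in SAP 8.1, 8.2 (by reference to 8.1), 10.2.1 and 10.2.2.
- Severity of illness is a term in 8 of 8. SAP 3.8.1 defines it by the RSV score, which protocol 9.1.1 and 11.1.5 restrict to Parts A and B.
- Age group, the protocol's stratification factor, is a term in 0 of 8.
- None names a comparison of each dose with placebo.

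The same severity factor is in the subgroups (SAP 6.6) and in the missing-baseline imputation (SAP 10.2.1).

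**Step 5. Check the outputs.** Three Part C tables (14.2.1.3.1.1, 14.2.1.3.2, 14.2.1.3.3) and two Part C figures (14.2.1.3.1.2, 14.2.1.3.1.3) report the RSV Clinical Scoring System. The clinician ReSVinet has no SAP section, table, figure or listing.

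**Step 6. Check the form of the DAVG model.** DAVG reduces each subject's swabs to one value. A random subject effect (SAP 10.2.1) cannot then be separated from the residual, so the term is redundant.

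**Step 7. Ask why the texts differ.** SAP section 14 lists the move to the mITT Population and to DAVG as changes from the protocol. The current protocol already contains both (11.1.1, 11.1.3). The SAP was therefore apparently written against an earlier protocol. This is an inference, since the protocol's date is not in the text supplied.

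**The case against.** The strongest reply is that this is an update in progress. Each part is reported separately, v2.0 was issued for Part A, and the protocol already commits the sponsor to sign Part C amendments before lock and unblinding. The documents cannot show whether such an amendment exists. All of this stands, and it rules out calling the mismatch a breach. It does not correct the text: section 11.1 of the protocol sets a deadline and supplies no content.

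Several narrower objections also stand in part:
- The SAP's treatment-group term could hold three levels, and the protocol's own ANCOVA wording likewise speaks of RV521 against placebo. A reader might infer that the SAP model excludes per-dose estimates. What can be said is that the SAP describes one RV521 arm and states no dose contrast.
- A reader might infer that the protocol leaves the primary contrast open. It does not; only the covariates are open.
- A reader might infer that Part C has no severity data. Respiratory rate, wheezing and retractions are recorded (protocol Appendix 17.4), and general condition is in the clinician ReSVinet (17.6). The grades differ and no mapping to the RSV score is given, so the SAP's factor cannot be computed as defined.
- The imputation point is minor. The mITT requires a centrally confirmed positive before treatment, so few analysed subjects should lack a baseline.
- A 6-dose criterion does appear for Part C in protocol 8.4.5, but for replacing subjects, not for deciding who is in the mITT.
- The counts of eight repeat one mismatch across tables. They show its reach, not an effect on any result.

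**Conclusion.** The point holds and must be settled before Part C database lock and unblinding. As supplied, SAP v2.0 conflicts with the protocol on arms, size, primary endpoint, strata, clinician scale, analysis population and last visit. All eight unredacted Part C ANCOVA models need a factor that cannot be formed as defined and omit the stratification factor.

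This assumes that v2.0 is the SAP in force for Part C. If an aligned amendment is already signed, confirming that closes the point.

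Two stronger conclusions are tempting. A reader might infer that the primary endpoint was switched in the light of results, or that the Part C analysis is already compromised. Nothing in the documents shows Part C data being seen before the endpoint was set, and the deadline for amending is tied to lock and unblinding. A reader might also count the lack of adjustment for two doses (SAP 6.1) as part of this error. With two 0.05 tests sharing one placebo arm (correlation 0.5), the familywise error is about 9.1%. The protocol sized Part C at 0.05 per comparison, however, and whether to control that rate is a separate decision for the sponsor. No bias figure is claimed for the 6-dose step, because the documents give none.

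**What to change.** If no Part C amendment exists, sign one before Part C lock and unblinding.

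1. Make RT-qPCR DAVG to Day 7 the Part C primary endpoint. Analyse it by ANCOVA with three treatment levels, each dose compared with placebo, and age-group stratum and baseline log10 viral load as terms. Drop the random subject effect. Co-pathogen status and symptom duration may stay as covariates; symptom onset is recorded in Part C (protocol 9.1.1).
2. For Part C, remove the RSV-score severity factor from the strata, subgroups, models and missing-baseline imputation (SAP 3.8.1, 6.6, 8.1, 8.2, 10.2.1, 10.2.2). Leave the Part B imputation alone, since the score is collected there. If a severity covariate is wanted, define it on the baseline clinician ReSVinet.
3. For Part C, analyse the clinician ReSVinet in place of the RSV Clinical Scoring System, compare each dose with placebo in the Wilcoxon analyses (SAP 8.3), and use the protocol's Part C mITT. Read that population alongside the replacement rule in protocol 8.4.5.
4. Reconcile the remaining Part C text with the protocol: objectives and endpoints (3.4, 4.4), design and numbers (3.5, 3.6.1, 3.7, 3.9), expected hospital stay (3.6.2), visit, swab and PK schedules (Tables 3 to 5), and the table, figure and listing indexes (19 to 21). The swab schedule matters most, because it feeds DAVG.

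The cost is document work only: no new data, subjects or visits, and no change to the protocol's 90% power at 34 evaluable per arm. A power cost arises only if the sponsor separately chooses to control familywise error; testing each dose at 0.025, for example, gives 84.0% instead of 90.2% at 34 per arm.
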